3.2 Sample Size and Power Considerations

No formal sample size is calculated for this study. This registry study will enroll all eligible subjects over a minimum of 2 years.

3.3 Randomization

This is an open-label, single-arm study with no randomization.

3.4 Changes to the Design and Study Procedures Proposed in Protocol

None.

4. ANALYSIS POPULATIONS

The analysis populations used to assess the results of this study are described.

4.1 All Patients Population

The All Patients population will include all patients who signed informed consent.

4.2 As-Treated (AT) Population

The as-treated population, defined as all subjects who fulfill all eligibility criteria, had an informed consent form signed either by the patient or a legal guardian, are enrolled and receive at least one dose of Revcovi, will be the primary analysis set in all analyses. For the derivation of the AT population, the eligibility criteria will be used as collected in the eCRF.

5. GENERAL ANALYSIS CONSIDERATIONS

All analysis will be descriptive and no statistical hypothesis will be tested. Descriptive statistics for continuous variables will include number of observations (n), mean, standard deviation (SD), median, minimum (min), and maximum (max); for categorial variables counts and percentages for each category. Ninety-five percent confidence intervals (CIs) will be calculated for the main outcome variables without adjustment for multiplicity to generalize the results to the general population. If not otherwise noted, confidence intervals for continuous variables will be based on normal distribution, for categorial variables on Clopper-Pearson (Clopper and Pearson 1934). Confidence intervals for Poisson distributions will be calculated by the method of Ulm (Ulm 1990).

Time to event analyses will be performed by the Kaplan-Meier method (Kaplan and Meier 1958). Confidence intervals for the median survival time will be calculated based on the method of Brookmeyer and Crowley (Brookmeyer and Crowley 1982) after log-log transformation.

All analyses will be performed by subject status (Adagen-Naïve subject, Adagen-Transitioning subject, or STP-2279-002 participant) and overall. Subject status is as collected on the Adagen/Revcovi Treatment page in the eCRF. There is a different recommended visit schema for the Adagen naïve subjects and the Adagen transitioning subjects (Table 1 and Table 2). However, a data review revealed that the timing of the assessments is not following the suggested visit schema. Therefore, the slotting schema within each subject status will be uniform for all assessments. All assessments will be slotted to the closest visit suggested for the Adagen transitioning or Adagen naïve subjects, respectively, regardless of whether or not the specific assessment is recommended for this visit, Participants of the STP 2279-002 study will be analyzed per the Suggested Schedule of Assessments for Adagen-Transitioning Subjects. Therefore, the visit windows will be specific for each type of subjects (see Section 13.3). All visits will be included in the overall column, regardless of whether or not the specific visit is analyzed for all type of subjects.

For the subjects transitioning from the STP-2279-002 study, the assessments during the STP-2279-002 study will be included in the data listings; however these assessments will not be included in the effectiveness or safety summary tables, because these results are already documented in the report of the STP-2279-002 study.

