7. EFFICACY ANALYSIS

The as-treated (AT) population will be used for all efficacy analyses. All efficacy data will also be listed.

All efficacy analyses will be descriptive (i.e., no statistical testing and no reported p-values), although 95% confidence intervals (CI) will be presented to show the variability of estimates as indicated below.

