The number of hospitalizations will be analyzed similarly as the infections, i.e. number of hospitalizations, number and percentages of hospitalized subjects, incidence rates of hospitalizations for the time periods described above. The duration of hospitalizations will be described by descriptive statistics for continuous variables based on the number of hospitalizations. Subjects who are hospitalized in one analysis period and discharged from the hospital in the subsequent analysis period will be counted for the full hospitalization period (i.e. from admission to discharge) in the analysis period where they were hospitalized. All hospitalizations will also be presented in a data listing.

For subjects <18 years of age, height-for age and weight-for age and for patients between 24 months and 18 years of age, BMI-for age will be presented by z-scores at baseline and each intermediate collection time-point. Z-scores will be calculated programmatically based on reported age, gender, height and weight.¹ Z-scores and changes from baseline of z-scores to each visit (at which height and weight are assessed) will be summarized using descriptive statistics.

¹ http://www.cdc.gov/nccdphp/dnpao/growthcharts/resources/sas.htm

Overall survival will be analyzed by a Kaplan-Meier analysis. Kaplan-Meier survival curves will be plotted by subject status. Subjects who are alive at the end of the observational period will be counted as a censored observation. Observational period is the time from initiation of Revcovi until the date of study completion or study discontinuation (calculated as: date of study completion or study discontinuation – date of treatment initiation + 1 day) or from treatment initiation until the date of death, for subjects who die (calculated as date of death – date of treatment initiation + 1 day). Date of study completion or date of study discontinuation will be used as reported on the Patient Disposition page in the eCRF. For subjects transitioning from the STP-2279-002 study, overall survival will be calculated based on the date of the first dose of Revcovi in the STP-2279-002 study. If it is known that the subject died, but the date of death is unknown, it will be assumed that the subject died the day after their last assessment (whatever has been entered as last available date to the database, e.g. date of laboratory value, onset or resolution date of an AE, date of study discontinuation).

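### The only interval planned for overall survival is for the median; if mortality on treatment is low, the report will give no survival probability with its uncertainty

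*SAP*

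**What the plan says.** SAP 5 adopts the Kaplan-Meier method for time-to-event data and then names one interval: "Confidence intervals for the median survival time will be calculated based on the method of Brookmeyer and Crowley", after a log-log transformation. SAP 7.2.3 applies the method: "Overall survival will be analyzed by a Kaplan-Meier analysis. Kaplan-Meier survival curves will be plotted by subject status". It adds the censoring rule, "Subjects who are alive at the end of the observational period will be counted as a censored observation", and the time origin. Survival runs from the start of Revcovi, and for the Phase III participants "overall survival will be calculated based on the date of the first dose of Revcovi in the STP-2279-002 study". Nothing further is specified for survival.

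Two general sentences on intervals might seem to cover the gap. SAP 5 states "Ninety-five percent confidence intervals (CIs) will be calculated for the main outcome variables without adjustment for multiplicity", but it does not list those variables, and the methods that follow are for continuous, categorical and Poisson data. SAP 7 describes the efficacy analyses as descriptive, "although 95% confidence intervals (CI) will be presented to show the variability of estimates as indicated below". In the sections below it, intervals are stated for the biochemical measures (7.2.1), the immune measures (7.2.2) and infection rates (7.2.3). The survival paragraph states none.

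Elsewhere the documents plan a descriptive summary of survival status (Protocol synopsis), a listing of deaths (SAP 8.2) and withdrawals tabulated by reason (SAP 6.2). No sample size is set (Protocol 13.1, SAP 3.2).

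**The concern.** A median survival time exists only if the curve falls to 50%. If few subjects die, the one summary with a planned interval will be reported as not estimable, and the report will contain a high, flat curve with nothing to show how much it is worth. SAP 5 splits every analysis into three subject-status groups, so some of those curves may rest on very few people. A flat line in a small group looks like certainty while the data remain compatible with appreciable mortality. Even a median that is reached does not say what proportion survives 12 or 24 months, which is what a reader of this registry would ask.

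**Working it through.** The plan states no figure to reproduce. The check is over assumed group sizes and mortality.

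**Inputs from the documents.** Minimum follow-up: until the last enrolled patient has 24 months of treatment (Protocol 7.4). Longest period tabulated: 8 to 9 years (SAP 7.2.3). Exit for transplant or gene therapy, with AE and survival follow-up at 1 and 6 months after the last dose (Protocol 7.4). The only mortality statement concerns untreated disease (Protocol 5.1).

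**Assumptions.** Group sizes, death rates and exit rates below are all assumed. A group of 6 is suggested by the first study described in Protocol 5.3.2; that this is STP-2279-002 is itself an assumption.

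**Step 1. Reaching the median without censoring.** At least half the group must die: 3 of 6, 5 of 10, 10 of 20. With deaths binomial, P(deaths ≥ n/2) is:

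| True survival | n=6 | n=10 | n=20 |
|---|---|---|---|
| 90% | 1.6% | 0.16% | 0.0007% |
| 80% | 9.9% | 3.3% | 0.26% |

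Under a constant hazard, a true median at time T needs a hazard of ln 2 / T: 0.35 per year for T = 2, 0.14 for T = 5, 0.077 for T = 9.

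**Step 2. Reaching the median with censoring.** Simulation with exponential deaths, administrative censoring uniform from 2 to 5 or 2 to 9 years, with and without an exit hazard of 0.5 per year for transplant, and no delayed entry. Ranges are over n = 20, 30, 40 and both exit settings:

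| Deaths per year | Follow-up 2–5 y | Follow-up 2–9 y |
|---|---|---|
| 0.01–0.02 | 0.4–3% | 0.6–6% |
| 0.05 | 2–7% | 12–16% |
| 0.10 | 15–20% | 30–70% |

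Censoring raises the chance well above Step 1, because a late death among few at risk can take the curve to 50%.

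**Step 3. The lower limit for the median.** It is finite once the lower pointwise limit falls to 0.5. The log-log limits are S^exp(±1.96·se), with se = √[d/(n(n−d))] / |ln S|. One death in 6: S = 0.833, se = 0.1826/0.1823 = 1.001, exp(1.96 × 1.001) = 7.12, limits 0.833^7.12 = 0.27 and 0.833^(1/7.12) = 0.97. One in 10 gives 0.47 to 0.99. So in a small group one death can make the lower limit finite. Without censoring, a group of 20 needs 5 deaths. With no deaths, neither the median nor its limits can be estimated.

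**Step 4. What a fixed-time estimate would show (no censoring before that time).** One death in 20: 95%, log-log interval 69.5 to 99.3%. Two in 20: 90%, 65.6 to 97.4%. No deaths: the log-log interval is undefined, and the exact 95% lower limit is 0.025^(1/n), which is 83.2% (n = 20), 69.2% (n = 10) or 54.1% (n = 6).

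**Step 5. Survival that is guaranteed.** Time runs from first Revcovi dose, but enrolment is the date of consent. Protocol 7.1 admits Phase III participants and subjects who started Revcovi earlier, with retrospective data. Protocol 5.3.2 describes five subjects treated for over 135 weeks, that is 135 × 7 = 945 days, against 730 days for a 24-month landmark. If these are the STP-2279-002 participants, anyone who enrols after that length of treatment has passed 24 months before entry and could not have died in the registry by then.

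**The case against.** The strongest reply is that a reader could infer too much: that the median will not be reached in any group, and that survival therefore yields neither an estimate nor any precision. The documents do not support this. They give no on-treatment mortality, sample size or death count, and Step 2 shows a real chance of reaching the median at higher mortality or longer follow-up. The binomial figures in Step 1 ignore censoring. A Kaplan-Meier curve is itself an estimate at every time, and a status summary, a death listing and withdrawal reasons are also planned. In small groups the median's lower limit is often finite: at 90% survival without censoring, at least one death occurs with probability 1 − 0.9^6 = 47% (n = 6) or 1 − 0.9^10 = 65% (n = 10). All of this stands, and it limits the claim.

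It can also be said that this is a descriptive registry, that the synopsis promises only a summary of subject status, and that the choice of tabulated quantities belongs in output shells. That carries less weight. The SAP has chosen an interval for survival, and has chosen the one least likely to be informative at low mortality. A finite lower limit for a median does not give survival at a chosen time.

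The last objection, that fixed-time estimates from first dose would present guaranteed survival as evidence, is correct and changes the remedy.

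**Conclusion.** The point holds in a limited form. The median is the only survival quantity for which an interval is named, and no fixed-time probability with its uncertainty is specified. The general interval sentences do not supply one. If mortality on treatment is low, at an assumed 0.01 to 0.02 deaths per year in 20 to 40 subjects, the median is reached in at most about 6% of simulated studies, and the report would state no survival probability with an interval. At higher assumed mortality the planned summary may be estimable, so non-attainment is likely rather than certain. The gap lies in what is reported. It does not show that the Kaplan-Meier method or the censoring rule is wrong.

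**What to change.** In SAP 5 and 7.2.3:

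- Report Kaplan-Meier survival probabilities at fixed times, for example 12 and 24 months, with log-log 95% intervals and numbers at risk, by subject status and overall. Add later times only where enough subjects remain at risk, with the threshold set in advance. This matters because SAP 2.1 includes subjects expected to have 3 to 4 months of therapy before transplant or gene therapy. With the 6-month follow-up, they are observed for about 9 to 10 months.
- Where a group has no deaths by that time, give an exact binomial lower limit on the number at risk, counting only subjects followed in the registry over the whole interval.
- Report the median and its interval only if the median is reached.
- Let subjects whose first Revcovi dose precedes enrolment (STP-2279-002 participants and retrospective starters) enter the risk set at the consent date, or show the estimates without them. For a group that enters after a given time, state that survival to that time cannot be estimated from the registry.

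The cost is SAP wording and one entry-time variable from a date already recorded. The estimates and intervals are standard output, and no new data are needed.

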6. STUDY POPULATION SUMMARY AT SCREENING

The study population will be summarized based on the as-treated population. All summaries in this section describe the subjects at the time of enrollment. All summaries will be by subject status (Adagen-Naïve subject, Adagen transitioning subject or STP-2279-002 participant) and overall. All data of the as-treated population set will also be listed.

6.1 Changes to the Planned Population Summarization Proposed in Protocol

None.

6.2 Subject Disposition

Number of subjects who signed informed consent, number of subjects fulfilling all inclusion/exclusion questions (based on the criteria in the eCRF), subjects in the as-treated set, subjects who completed the study, subjects who underwent a transplantation, and subjects who discontinued from the study will be summarized using counts and percentages. Subjects who withdrew from the study will also be summarized using descriptive statistics by reason for withdrawal.

Subjects who do not fulfill the eligibility criteria will be listed with the reason for not fulfilling the eligibility criteria.

6.3 Demographics

The continuous variable of subject's age at study entry (reported start date of Revcovi in the CLI-06814AA1-01 study) will be summarized using descriptive statistics. The continuous variables of weight, height, and body mass index (BMI) will be summarized using descriptive statistics for the last available data prior to or on the date of reported start date of Revcovi in the CLI-06814AA1-01 study. The categorical variables of subject's gender, race, and ethnicity will be summarized using counts and percentages for each category. Missing categories will be presented if applicable.

6.4 Disease Background and History

Disease background will also be summarized at screening by subject status and overall. Missing categories will be presented if applicable. Disease background includes age at first diagnosis of ADA-SCID (years), time from first diagnosis of ADA-SCID to start of Revcovi treatment in the STP 2279-002 study, if applicable, (months), and availability of ADA-SCID mutations. All parameters will also be listed. Missing categories will be presented if applicable.

6.5 Medical History

Medical history at screening will be listed, but not summarized.

6.6 **Prior ADA-SCID Treatment excluding ERT**

The number and percentages of patients who received prior ADA-SCID treatment (excluding ERT) will be summarized by type of treatment and overall. Free text for other treatments will be listed but not summarized.

6.7 **Prior ERT Treatments**

Prior ERT medications (Adagen treatment) will be summarized for all subjects transitioning from Adagen to Revcovi and for the STP 2279-002 subjects. The following parameters will be summarized: duration of Adagen treatment (i.e. last dose – first dose +1 day), units per administration, administration frequency, total weekly dose (as reported on the eCRF) and calculated total weekly dose per kg body weight for the prescribed and actual dose. For subjects who were treated according to the prescription, actual dose will be derived from the prescribed dose. The number and percentages of subjects who stopped Adagen treatment prior to the first dose will also be reported together with summary statistics for the time from the last dose of Adagen until the first dose of Revcovi. For the STP 2279-002 subjects, the duration of treatment with Revcovi in the STP 2279-002 study (last dose – first dose of Revcovi in the STP 2279-002 study + 1 day) will be summarized. All prior treatments with Adagen will also be presented in a data listing.

6.8 **Physical Examination**

Physical examination results at screening will be reported as medical history and will be analyzed and presented as such.

6.9 **Protocol Deviations**

A full list of protocol deviations will be presented in the clinical study report. Because this is a registry with no scheduled assessments or planned treatments, on-study protocol violations are restricted to administrative and operational deviations (e.g. delayed reporting of an SAE or transmission of clear names together with SAE reports). Protocol deviations will be listed but not summarized.

7. EFFICACY ANALYSIS

The as-treated (AT) population will be used for all efficacy analyses. All efficacy data will also be listed.

All efficacy analyses will be descriptive (i.e., no statistical testing and no reported p-values), although 95% confidence intervals (CI) will be presented to show the variability of estimates as indicated below.

7.1 Changes to the Planned Efficacy Analysis Proposed in Protocol

None.

7.2 Efficacy Endpoint and Analysis

7.2.1 Biochemical assessments

Biochemical assessments to adjust Revcovi dosing throughout the study include trough plasma dAXP and ADA activity, which will be assessed from trough plasma samples obtained during the study. Summary statistics for the absolute value and the changes from baseline will be calculated for plasma dAXP and ADA activity for all time points. 95% CIs for the means will be calculated for each time point based on the normal distribution function for the actual values and the changes from baseline. For subjects transitioning from the STP 2279-002 study, baseline is defined as the last available value prior to the initiation of Revcovi in the STP 2279-002 Study. The mean and its standard error (SE) for the plasma dAXP and ADA activity for all suggested time points will be plotted by the subject status. The number and percentages of subjects (including 95% CIs) maintaining an erythrocyte dAXP concentration of $\leq 0.02 \mu$ mol/ml will be calculated for each time point. Also, the number and percentages of subjects (including 95% CIs) maintaining a trough ADA activity of $\geq 30 \mu$ mol/h/ml will be calculated for each time point.

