7.2.2 Immune status assessments

Immune status will be assessed by the following end points:

- absolute lymphocyte count
- lymphocyte subset (B, T, and NK) analysis: the number of cells for each subset will be determined by fluorescence-activated cell sorter (FACS) using the following panel:
 - CD3+ (Mature T cells) Percent and Absolute
 - CD3+ CD8+ (Suppressor T Cells) Percent and Absolute
 - CD3+ CD4+ (Helper Cells) Percent and Absolute

- CD (16+56) + (NK Cells) Percent and Absolute
- CD19+ (B Cells) Percent and Absolute
- Absolute Lymphocytes (CD45+)
- %CD4 (Helper Cells)/% CD8 (Suppressor T Cells)
- Quantitative immunoglobulin (Ig) concentration (IgG, IgA, IgM).

The absolute values and the changes from baseline for all endpoints for immune status will be summarized by descriptive statistics for all time points. 95% CIs for the means will be calculated for each time point based on the normal distribution function for the actual values and the changes from baseline. Baseline for the STP 2279-002 transitioning subjects will be handled the same as for the biochemical assessments.

It is recommended that Investigators consider a measurement of immune response (PHA stimulation or equivalent). These data will be listed but not summarized.

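### The 95% CIs for means and changes from baseline are tied to the normal distribution with no t quantile named, so as written they are too narrow in small by-visit, by-status cells

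*SAP*

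**What the plan says.** SAP 5 (General Analysis Considerations) sets the default: "confidence intervals for continuous variables will be based on normal distribution". SAP 7.2.1 applies it to dAXP and ADA activity, for actual values and for changes from baseline: "95% CIs for the means will be calculated for each time point based on the normal distribution function for the actual values". SAP 7.2.2 does the same for lymphocyte counts, subsets and immunoglobulins: "95% CIs for the means will be calculated for each time point based on the normal distribution function". No section of the SAP or the protocol mentions a t distribution or t quantile.

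On grouping, SAP 5 says "All analyses will be performed by subject status"; the statuses are Adagen-naïve, Adagen-transitioning and STP-2279-002 participant, with an overall column added. On size, SAP 3.2 says "No formal sample size is calculated for this study".

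On purpose, SAP 5 says that the 95% intervals "will be calculated for the main outcome variables without adjustment for multiplicity to generalize the results to the general population", and SAP 7 adds that "95% confidence intervals (CI) will be presented to show the variability of estimates as indicated below".

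**The concern.** When the SD is estimated from the same few subjects, the standardised mean follows a t distribution with n−1 degrees of freedom, not a normal one. An interval built with the normal quantile then covers the true mean less often than its label says, even if the data are perfectly normal. The shortfall is trivial in large cells and substantial in cells of a few subjects.

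At stake is the honesty of the error bars on mean dAXP, mean ADA activity, lymphocyte subsets, immunoglobulins and their changes from baseline. The SAP gives these intervals a purpose beyond description of the sample, and an interval that is too narrow overstates how precisely the registry has estimated those means. There is also a reproducibility issue. SAP 5 names its other methods exactly (Clopper-Pearson, Ulm, Brookmeyer-Crowley after log-log transformation), while two programmers could implement the rule for means differently.

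**Working it through.** **Inputs.** The nominal level is 95% (SAP 5). The interval basis is the normal distribution (SAP 5, 7.2.1, 7.2.2). The documents give no cell size, so every n below is an assumption, shown over a range. The plan states no achieved coverage; the only figure to test is the nominal 95%.

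**Formula.** Under the literal reading the interval is mean ± 1.96 × s/√n. For normal data, coverage = 2·F(1.96; n−1) − 1, where F is the t distribution function. The correct multiplier is t(0.975, n−1), and the width ratio is that multiplier divided by 1.96.

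**Hand check.** At n=3 (2 df) the formula reduces to 1.96/√(2 + 1.96²) = 1.96/√5.8416 = 0.811.

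| Assumed n | Coverage of mean ± 1.96 SE | t(0.975, n−1) | t width ÷ normal width |
|---|---|---|---|
| 40 | 94.3% | 2.023 | 1.03 |
| 30 | 94.0% | 2.045 | 1.04 |
| 20 | 93.5% | 2.093 | 1.07 |
| 10 | 91.8% | 2.262 | 1.15 |
| 6 | 89.3% | 2.571 | 1.31 |
| 3 | 81.1% | 4.303 | 2.20 |
| 2 | 70.0% | 12.706 | 6.48 |

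Coverage first reaches 90% at n=7 and 94% at n=30. Simulation with 400,000 normal samples per n gave 93.6%, 91.9%, 89.2% and 81.3% at n=20, 10, 6 and 3. With t quantiles it gave 95.0% at each.

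**Are small cells plausible?** The documents give no counts, but several features point that way:
- Protocol 5.1 puts incidence between 1:200,000 and 1:1,000,000 live births.
- SAP 2.1 includes subjects expected to have only 3 to 4 months of enzyme replacement before transplantation or gene therapy, while the visit windows in SAP 13.3 run to TM 108.
- Immune-status assessments are optional (SAP 2.2), the visit schedule is not binding, missing data are not imputed (SAP 13.3), and a change from baseline also needs a baseline value.
- The overall column does not always enlarge n. SAP 5 says "All visits will be included in the overall column, regardless of whether or not the specific visit is analyzed for all type of subjects". In SAP 13.3, seven visits (TW 2, TW 6, TW 10, TM 4, TM 5, TM 7, TM 8) appear only in the Adagen-naïve table, so overall there means Adagen-naïve subjects alone. This is context, not an error.

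**Skewed data.** For an assumed lognormal variable (200,000 runs), coverage was:

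| Assumed n | Log-SD | Normal quantile | t quantile |
|---|---|---|---|
| 6 | 0.5 | 85.9% | 91.7% |
| 6 | 1.0 | 76.2% | 82.5% |
| 20 | 0.5 | 91.6% | 93.1% |
| 20 | 1.0 | 85.2% | 86.7% |

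The t quantile helps in each case but does not restore 95%.

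**The case against.** The strongest reply is that the wording may only state the distribution assumed for the data, which is also the assumption behind a t interval. SAP 5 lists a basis for each data type in one sentence and gives no formula and no 1.96. That is possible. But sections 7.2.1 and 7.2.2 refer to the normal distribution function as the basis of the interval, which more naturally means the normal quantile. If t was meant, the text still needs to say so.

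Second, all the n are assumed, and at n=20 to 40 the shortfall is only 1.5 to 0.7 percentage points (95 − 93.5; 95 − 94.3). The largest shortfalls fall where no interval is informative; at n=2 the t interval is 6.48 times as wide. Nor does every cell exist. Study days for STP-2279-002 participants run from their first dose in that study (SAP 13.2), and assessments made during it stay out of the summary tables (SAP 5), so that group may have no early post-baseline summaries. All of this stands and limits the size of the problem.

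Third, under strong skewness the quantile is the smaller part of the shortfall. This also stands, and it is why the fix carries a caution.

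Fourth, little depends on these intervals. There are no tests, p-values or statistical stopping criteria; n, mean, SD, median and range are reported and all efficacy data are listed. This sets the weight of the point but does not make the stated rule right.

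A reader might go on to infer that the Poisson intervals for infection and hospitalization rates (SAP 7.2.3) are also too narrow. The documents do not support that: they give no event rate and no between-subject variation, and the SAP already states the Poisson assumption.

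**Conclusion.** The point holds as a defect in the written rule with limited consequence. Taken literally, SAP 5, 7.2.1 and 7.2.2 produce intervals labelled 95% that cover 93.5% at n=20, 91.8% at n=10, 89.3% at n=6 and 81.1% at n=3. This rests on the literal reading, on normally distributed data and on assumed cell sizes; the arithmetic is exact.

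A reader might infer that the reported intervals will certainly be wrong, or that cells of three or six subjects are known to occur. Neither follows, because the SAP gives no formula and no counts. Nor is any study conclusion overturned. The target-attainment percentages, which fall under the Clopper-Pearson rule, and the Kaplan-Meier survival analysis are unaffected. The rule is worth correcting because a t interval is at least as good under either reading.

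**What to change.** In SAP 5, state that 95% CIs for means and for changes from baseline are calculated as mean ± t(0.975, n−1) × SD/√n, where n is the number of subjects contributing to that cell, and that no CI is given when n<2. In 7.2.1 and 7.2.2, replace the reference to the normal distribution function with a cross-reference to that rule. Add a table footnote that for skewed variables the interval is approximate and should be read with the median and range.

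The drafting cost is one rule, two cross-references and a footnote. The statistical cost is width: 1.07, 1.15, 1.31 and 2.20 times at n=20, 10, 6 and 3. Skewness remains uncorrected. SAP 10 reports that an interim analysis has already presented biochemical assessments, lymphocyte subsets and immunoglobulins. If CIs were computed there with the normal quantile, they would not be directly comparable with the final ones, and the report should say so. If t intervals were already intended, this is a wording change only.
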